7.5.2 Study Stopping Criteria

If ≥ 2 device-related SAEs or ≥ 3 device-related severe TEAEs (grade 3) in the same SOC PT are observed, further enrollment and treatment will be discontinued. Subjects on trial at the time on discontinuation will continue to be followed per protocol.

7.5.3 Investigator Decision to Discontinue Subject Use of Device

A subject may be removed from the study for the following reasons post initial device use; however, whenever possible the subject should be followed for safety evaluations per protocol:

• Study non-compliance to protocol requirements that in the opinion of the participating clinical site PI or appropriate sub-investigator poses an increased risk (e.g., missing safety labs) or compromises the validity of the data.

• Lost to follow-up. A subject will be considered lost to follow-up if he or she fails to appear for a follow-up assessment. Extensive effort (i.e., generally three documented contact attempts via telephone calls, e-mail, etc., made on separate occasions) will be made to locate or recall the subject, followed by a couriered delivery of study documents to the subject's home address to determine the subject's health status. These efforts will be documented in the subject's study file.

• Medical disease or condition, or new clinical finding(s) for which continued participation, in the opinion of the participating clinical site PI or appropriate sub-investigator, might compromise the safety of the subject, interfere with the subject's successful completion of this study, or interfere with the evaluation of safety.

• If any TEAE, clinical laboratory abnormality or situation occurs such that continued participation in the study would not be in the best interest of the subject.

- The occurrence of a SAE.
- If the subject is using the device in any manner inconsistent with instructions and protocol directives and procedures.

If the subject agrees, every attempt will be made to follow all TEAEs through resolution or stabilization.

Subjects who withdraw or are lost to follow-up after signing the informed consent form (ICF) and use the RD-X19 device will not be replaced. Subjects who withdraw or are withdrawn from this study after signing the ICF during screening but before randomization will be replaced.

The reason for subject discontinuation or withdrawal from the study will be recorded on the appropriate e-CRF.

Confidential Information; this Protocol is Confidential and Proprietary to EmitBio Inc.

	Page 35 of 70
EmitBio Inc.	Version: 3.1
EB-P30-01	7 February 2024

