7.5 Device Discontinuation

7.5.1 Study Pausing Criteria

If observations of any potential device-related SAE or patterns of non-resolving device-related TEAEs with severity grade 2 or higher in the same System Organ Classification Preferred Term (SOC PT) are observed in a single subject, treatment will be discontinued for that subject and they will continue with the full study schedule including collection of all data as if they had continued to be treated.

EB-P30-01 enrollment may be paused if any of the following events occur:

- Any subject experiences a device-related SAE.
- Any subject experiences laryngospasm, bronchospasm, or anaphylaxis within 2 hours after treatment.
- Two (2) or more subjects experience an allergic reaction such as generalized urticaria (defined as occurring at three or more body parts) within 72 hours after treatment.
 - Potential photo-allergy or phototoxicity to one or more photosensitizing drugs in the subject's medical history should be investigated in all cases. See "Medications that Increase Sensitivity to Light: A 1990 Listing (Levine 1990)."
- Three (3) or more subjects experience a Grade 2 or higher TEAE within the same SOC PT based on the Medical Dictionary for Regulatory Activities (MedDRA) coding, considered to be related to RD-X19.

While the study is paused, a complete review of safety findings will be performed by an Independent Medical Monitor at the earliest opportunity and will make a recommendation to the Sponsor regarding continuation or termination of all or some of the study subjects and/or the overall study protocol. The Independent Medical Monitor has no affiliation with the design or conduct of the trial. The recommendation will be taken under advisement by the study Sponsor who has responsibility for any final decision.

A study volunteer may elect to discontinue participation in the trial at any time. Investigative staff will ask the volunteer to return for an early termination evaluation, but they are under no obligation to do so. All study subjects must return the RD-X19 device at study termination and

	Page 34 of 70
EmitBio Inc.	Version: 3.1
EB-P30-01	7 February 2024

study staff must verify that the device serial number matches the study subject to whom it was assigned.

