7.5.4 Follow-up of Study Subjects Who Discontinue Device Use

Discontinuation of study device use does not constitute discontinuation from the study, and the study procedures should be completed as indicated by the Study Schedule of Activities. If a clinically significant finding is identified, including, but not limited to, changes from baseline (Day 1), after enrollment, the participating clinical trial site PI or qualified designee will determine if any change in subject management is needed. Any new clinically relevant finding will be reported as a TEAE.

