8.4 Procedures for Clinically Significant Findings

If in the judgement of the PI any finding poses a previously unknown risk to an individual or leads to a diagnosis of a disease or condition that would have disqualified the individual for enrollment, the study subject will be withdrawn from the study immediately.

All clinically significant findings that occur post randomization and after the first use of the RD-X19 device will be considered TEAEs.

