- 3) Those who progress to moderate disease indicated by new onset shortness of breath (respiratory rate ≥20/minute) and SpO2 of < 96% confirmed by pulmonary imaging or lower airway disease diagnosed by pulmonary imaging involving < 50% of lung parenchyma;

- Those who progress to severe disease with respiratory rate >30/minute and/or O2 saturation ≤93% on room air or lower airway disease confirmed by pulmonary imaging involving ≥ 50% of lung parenchyma;
- 5) Those who require hospitalization for severe COVID-19;
- 6) Those who require endotracheal ventilation or ECMO with or without the use of solumedrol; and
- 7) Those who die.
- Subjects with a primary care, urgent care, or emergency room visit that are not hospitalized as a result of their medical consultation, may continue treatment with the investigational device and should attend regularly scheduled follow up visits per protocol. Subjects that are admitted to the hospital should discontinue all treatment in lieu of standard of care for severe/critical COVID-19 illness or other SAEs. Such subjects' endpoint data will be right censored as specified in the Statistical Analysis Plan (SAP).
 - Subjects who are treated with any FDA-authorized COVID-19 therapy will discontinue treatment but will continue to be followed per protocol. Such subjects' endpoint data will be right censored as specified in SAP.
 - Subjects who first reach clinical resolution on or after study day 11 should be scheduled for their day 14 visit, which has a +/- 2 day window, so that a total of five consecutive visits (including the first resolution visit) are captured where resolution *may* be observed thus allowing the primary clinical sustained resolution endpoint to be met. Under no circumstances, however, may a study subject be scheduled for their day 14 visit beyond study day 16.

	Page 46 of 70
EmitBio Inc.	Version: 3.1
EB-P30-01	7 February 2024

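### Protocol 7.5.3 lets investigators remove subjects from the study where stopping the device would suffice, so unresolved subjects are censored early (effect probably small)

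*Protocol*

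**What the plan says.** Protocol 7.5.3 carries a heading about the investigator stopping device use. Its operative sentence goes further: "A subject may be removed from the study for the following reasons post initial device use". One listed reason is "If the subject is using the device in any manner inconsistent with instructions and protocol directives and procedures". Others are non-compliance that the investigator thinks undermines data validity, and any SAE. For subjects so removed, the section names safety evaluations and TEAE follow-up. It does not mention the e-diary or the antigen tests.

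Elsewhere the general rule is to stop treatment and keep following:

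- 7.5.1, for a potential device-related SAE or a non-resolving pattern of device-related TEAEs in one subject: "treatment will be discontinued for that subject and they will continue with the full study schedule including collection of all data".
- 7.5.2, if the stopping criteria are met: "Subjects on trial at the time on discontinuation will continue to be followed per protocol".
- 7.5.4: "Discontinuation of study device use does not constitute discontinuation from the study".
- 8.6: "Subjects who are treated with any FDA-authorized COVID-19 therapy will discontinue treatment but will continue to be followed per protocol".

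Protocol 8.4 is a separate, mandatory exit for certain findings judged by the PI: "the study subject will be withdrawn from the study immediately".

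On analysis, Protocol 9.4.1 and SAP 8.2 apply four rules in order: hospitalized subjects are censored at 360 hours; sustained resolution is an event; subjects who take nirmatrelvir/ritonavir or molnupiravir first are censored at that time; everyone else is censored at the last e-diary entry.

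**The concern.** If the investigator only stops the device, 7.5.4 applies and assessments continue. If the investigator uses the removal option, no text says they continue, because 7.5.4 covers subjects who stop the device and not subjects who leave the study. Such a subject stays in the FAS, and a sustained resolution already recorded still counts. Without one, and without hospitalization or a named antiviral, the subject is censored at the last e-diary entry. The key secondary endpoint likewise censors at the last test (SAP 8.3.1 iii).

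That censoring is non-informative only if removal is unrelated to how soon the subject would have recovered. Removal at the investigator's discretion during a short illness need not meet that condition. If it also differed by arm, the hazard ratio would be biased. The loss is avoidable, because the diary and tests are already scheduled through Day 14. Removal is also not needed to deal with poor exposure: SAP 5.3 already excludes subjects with fewer than seven treatments from the per-protocol population.

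**Working it through.** **Who is affected.** Starting from the 7.5.3 reasons:

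1. Sustained resolution already recorded, with no recurrence or progression while on study: event kept, no early censoring.
2. Hospitalized: censored at 360 hours, overriding all else. Hospitalization is itself an SAE criterion (Protocol 8.6.5).
3. Potential device-related SAE: 7.5.1 is mandatory and specific, and full data collection continues.
4. Took a named antiviral first: censored at that time under rule (iii).
5. Remaining subjects: censored at the last e-diary entry. Through the SAE reason, these are mainly subjects whose SAE is neither a hospitalization nor potentially device-related.

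In the SAP 8.2.5 sensitivity analysis, group 5 keeps last-diary censoring, except that subjects who progress to more severe COVID-19 or need any FDA-authorized COVID-19 therapy move to 360 hours.

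**The plan's own figures** (Protocol 9.2; one-sided 0.025, 1:1). Schoenfeld: D = 4(z_α + z_β)² / (ln HR)².

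- HR 0.62, 95% power: 4(1.960 + 1.645)² / 0.2285 gives 228.
- HR 0.65, 90% power: 227. HR 0.69, 80% power: 229.
- Power at 228 events: 95.0%, 90.2% and 80.0%.
- Events: 163 × 0.90 + 163 × 0.50 = 228.2; 228 / 0.70 = 325.7, hence 326 subjects.

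The stated design reproduces.

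**Power if every event among removed subjects is lost.** Power = Φ(√D·|ln HR|/2 − 1.96). With an assumed 5% removed, D = 228 × 0.95 = 216.6 and power is 94.0%, 88.7% and 78.0% at HR 0.62, 0.65 and 0.69.

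**Assumed removal rates.** None is given. The nearest anchor is the earlier sham-controlled trial (Protocol 4.1), in which none of 31 subjects discontinued. The exact one-sided 95% upper limit is 1 − 0.05^(1/31) = 0.092. Rates of 2% to 10% are explored.

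**Simulation A.** 163 per arm, exponential times, pooled event proportion 70% by 336 h, removal uniform over 24–168 h, censoring at removal, treatment-only Cox Wald test. Slow means resolution after 168 h. 6,000 null and 3,000 other runs; Monte Carlo SE about 0.002 on type I error.

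**Simulation B.** Adds the 48 h confirmation. The last confirmable first success is 336 − 48 = 288 h, so the hazard is −ln(0.30)/288 = 0.00418/h (median 166 h). Removal uniform over 24–192 h, log-rank test. Slow means after 144 h; never means after 288 h. 20,000 null and 10,000 HR 0.62 runs; SE about 0.001 at 0.025.

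Null results (HR is sham to RD-X19, so below 1 favors RD-X19):

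| Removal | Simulation | HR | One-sided error |
|---|---|---|---|
| None | B | 1.00 | 0.025 |
| 5% both arms, slow | A and B | 1.00 | 0.025 |
| 5% RD-X19, 2% sham, slow | A | 0.99 | 0.030 |
| 2% RD-X19, 5% sham, slow | A | 1.01 | 0.020 |
| 10% RD-X19, 2% sham, slow | A | 0.97 | 0.043 |
| RD-X19 only, slow, 2/5/9% | B | 1.00/0.99/0.98 | 0.028/0.031/0.036 |
| RD-X19 only, never, 2/5/9% | B | 0.98/0.94/0.90 | 0.039/0.072/0.144 |
| Sham only, never, 5% | B | 1.06 | 0.010 |

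Power at HR 0.62 with 5% slow resolvers removed in both arms is 94.4% against 95.0% (B), and 94.9% both with and without removal (A).

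**Censoring removed subjects at 360 h instead (B, null).** RD-X19 only, never, 2/5/9%: HR 1.00 throughout, error 0.027/0.025/0.024. RD-X19 only, slow, 5%: HR 1.05, error 0.011.

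**The case against.** The strongest reply is that 7.5.3 sits within the section on device discontinuation, that its removal wording is permissive, and that 7.5.4 follows at once with the follow-up rule. Read together, one section gives the grounds and the next the follow-up. Removed subjects stay in the FAS, exit reasons are tabulated by arm (SAP 7.2), and censoring cases are counted (SAP 8.2), so an imbalance would be visible. Much of this stands: a site that reads the sections this way loses nothing. But 7.5.4 does not reach a subject actually removed from the study, and tables can show an imbalance without recovering the missing diaries.

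Four stronger readings are tempting, and the documents do not support them:

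- **Local reactions to blue light give a documented route to arm-related removal.** Protocol 5.2.1 lists such reactions as mild and transient but links them to neither misuse nor removal. Section 4.1 reports no local site reactions in the earlier trial of 31 subjects, 4.3 describes device-related TEAEs as very infrequent and mild, and 6.1 reports good tolerability at 32 J/cm². Double-blinding, observation of every treatment (4.3) and re-training (10.5) also limit differential removal.
- **The sensitivity analysis does nothing for removed subjects.** It already moves those who progress or need authorized therapy to 360 hours.
- **The exit reasons in SAP 7.2 show that removal for misuse is intended.** The list looks generic: for randomized subjects it includes screen failure, and also pregnancy, although 8.8 permits pregnant women to take part.
- **Type I error is materially inflated.** The 0.072 and 0.144 results need every removal to be on RD-X19 and every removed subject to be one who would never resolve. At 9% that is about 15 subjects (0.09 × 163), whereas Protocol 9.2 expects only about 16 RD-X19 subjects without an event (0.10 × 163).

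**Conclusion.** The inconsistency is real, and it permits avoidable and possibly informative censoring of the primary endpoint. The effect is probably small. Symmetric 5% removal leaves type I error at 0.025 and power at about 94% at HR 0.62. A 5% versus 2% imbalance among slow resolvers gives about 0.03, and the reverse imbalance is conservative. Clear inflation requires removal that is both tied to one arm and concentrated in non-resolvers, and nothing in the documents establishes either.

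These sizes rest on assumed removal rates and timing, a constant hazard, and unstratified log-rank or Cox tests in place of NPANCOVA. The pooled 70% event proportion was used because 90% and 50% would imply ln(0.5)/ln(0.1) = 0.30 under proportional hazards, not 0.62. This is a cheap improvement worth making and does not threaten the design.

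**What to change.** **Protocol 7.5.3.** For misuse, data-validity non-compliance and the SAE item, replace removal from the study with discontinuation of device use. State that 7.5.4 then applies: e-diary, temperature and SpO2, antigen tests and visits continue through the Day 14 visit unless the subject withdraws consent. State that 7.5.1 governs potential device-related SAEs. Keep study exit for loss to follow-up, safety or best-interest grounds, non-compliance that poses a risk, and 8.4 withdrawals.

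**SAP 8.2.5 (optional).** Add a sensitivity analysis that censors the remaining investigator-removed, unresolved subjects at 360 hours, identified from the recorded exit reasons. Note in the SAP that it is conservative against the arm with more removals if those subjects would have resolved.

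**Cost.** One wording change and, if wanted, one extra analysis. The assessments are already scheduled and exit reasons already collected. The downside is continued diary contact with a few subjects who are off treatment.

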7.5.4 Follow-up of Study Subjects Who Discontinue Device Use

Discontinuation of study device use does not constitute discontinuation from the study, and the study procedures should be completed as indicated by the Study Schedule of Activities. If a clinically significant finding is identified, including, but not limited to, changes from baseline (Day 1), after enrollment, the participating clinical trial site PI or qualified designee will determine if any change in subject management is needed. Any new clinically relevant finding will be reported as a TEAE.

8.0 STUDY ASSESSMENTS AND PROCEDURES

8.1 Screening Assessments

8.1.1 Screening Procedures

Subjects will provide written informed consent prior to initiating any screening procedures. At the screening visit, and prior to any other study-related activities, designated study personnel will provide the subject with detailed study information and will obtain written informed consent.

Subject numbers will be assigned with the three-digit numerical site number beginning with numbers greater than three hundred (e.g. 301) followed by an alphanumeric protocol identifier (P30) and finally a three digit unique numerical identifier assigned with each new subject (e.g. 001).

Example Subject Number: 301-P30-001

8.1.2 COVID-19 and Influenza A and B Screening

Individuals who identify with symptoms associated with mild COVID-19 present for 72 hours or less will be tested for the presence of SARS-CoV-2 and Influenza A or B using FDA-authorized rapid antigen diagnostic tests. These systems allow for rapid detection of SARS-CoV-2 and Influenza A and B via laminar flow immunoassays for the direct and qualitative detection of target antigens. All potential study subjects must be tested, regardless if they have a documented recent positive PCR or antigen test results for SARS-CoV-2.

Study volunteers will self-assess their COVID-19 symptoms as none (0), mild (1), moderate (2), or severe (3) during screening as part of a disease assessment questionnaire per guidance provided in protocol section 4.4.1, Symptom Severity Grading. Eligible subjects for enrollment must present with mild COVID-19 and test negative for Influenza A and B, and have at least two moderate or severe symptoms (cough, sore throat, nasal congestion, headache, chills and/or sweats, myalgia, fatigue, nausea (with or without vomiting) or at least one moderate symptom and an oral temperature of ≥ 100.5 °F are also eligible for enrollment. All eligible subjects must have had the onset of sign/symptoms ≤ 72 hours prior to consenting.

	Page 36 of 70
EmitBio Inc.	Version: 3.1
EB-P30-01	7 February 2024

- Potential subjects with any evidence of lower airway involvement, including shortness of breath either at rest on upon exertion, are ineligible for the study and should be referred to their primary care provider or urgent care center.
- Potential subjects with COVID-19 signs and symptoms reported more than 72 hours from onset are ineligible for the study and should be referred to their primary care provider or urgent care center.
- Potential subjects will also be asked to report if they have been previously diagnosed with COVID-19 via an FDA-approved diagnostic test and whether or not they report that they have been previously vaccinated against COVID-19. The date(s) of prior COVID-19 diagnoses and the number and approximate dates of COVID-19 vaccinations and the vaccine manufacturer will be documented. Asking potential subjects to bring the CDC (or national equivalent, if such exists for non-US subjects) COVID-19 vaccination card will ease the time and burden of this task.
- All vital sign measurements (HR, BP, RR, SpO₂%), should be assessed as three measures over a 10-minute period and the average value should be captured for the purposes of this clinical trial.
- A complete COVID-19 disease assessment will include vital signs recorded as part of general screening.
- Subjects will be asked to assess their loss of taste and loss of smell (binary assessments at each assessment*). and pose the following patient-reported global impression assessments on Days 5, 8 and 14:

a) In the past 24 hours, have you returned to your usual health (before your COVID-19 illness)? Yes or No

b) In the past 24 hours, have you returned to your usual activities (before your COVID-19 illness)? Yes or No

*COVID-related loss of sense of taste and loss of sense of smell are well understood to normalize over a prolonged period of time given the neurological etiology, long after SARS-CoV-2 has been eliminated from the body. As these signs of COVID-19 have been reported to vary with each variant, this information is being collected for informational purposes and will be assessed only as part of the qualitative patient reported global assessment and will not be included as a component of the primary efficacy endpoint.

	Page 37 of 70
EmitBio Inc.	Version: 3.1
EB-P30-01	7 February 2024

8.1.3 General Screening

Some or all of the following assessments are performed during the screening visit to determine eligibility requirements as specified in the inclusion and exclusion criteria:

- Obtain subject-reported medical history focusing on conditions per protocol exclusion criteria and those associated with an increased risk of progression of COVID-19 (Asthma, Cancer, Cerebrovascular Disease, Chronic Kidney or Liver Disease, Chronic Lung Disease, Tuberculosis, Diabetes Mellitus, Hypertension, Heart Disease, Recent Pregnancy, Immune Deficiency, Smoking, Physical Activity level, Mood Disorders). It is particularly important to capture and document medical conditions that include signs and symptoms of COVID-19 but that are not due to the current episode of COVID-19.
- History of exposure to someone with COVID-19 or participation in an event that poses a significant risk of exposure to SARS-CoV-2 (commercial flight, major sporting or entertaining events, etc) over the past two weeks, including start and end dates.
- Review all pre-study medications, vitamins, supplements, and therapies up to 14 days 0 prior to the start of screening that could impact the use of, or response to, the device and record on the appropriate source document. The use of any medications to treat any of the COVID-19-related symptoms (e.g., analgesics, antipyretics, decongestants) should be recorded and the name of medication, dose, dosage form, and date and time(s) of administration should be reported. Antibiotics are not indicated as a treatment for COVID-19 and use of antibiotics (e.g. tetracycline, azithromycin) for this purpose should be documented accordingly. Individuals receiving antibiotics for treatment of COVID-19 must discontinue use prior to study enrollment and this information should be documented. Individuals should be informed not to take antibiotics or other medications purported to treat COVID-19 (such as hydroxychloroquine or ivermectin) or known to treat COVID-19 (such as nirmatrelvir/ritonavir or molnupiravir) during their participation in the study. Antibiotic treatment of a bacterial infection during screening is a protocol exclusion because of the existence of an active concurrent disease. During the study, the decision to prescribe antibiotics for bacterial infections is a clinical decision that should be made by a licensed medical care provider outside of the protocol. Likewise, FDA authorized COVID-19 therapies for progressed COVID-19 are, of course, both appropriate and necessary when medically indicated but will result in study subjects being right censored for the efficacy analysis. These subjects will continue to be followed, per protocol, for safety assessments. Such use, and the reason for such use, will be documented. Study subjects will be requested to refrain from use of medications to treat COVID-19 symptoms. Any such use should be recorded on the concomitant medication form along with reason for use. The requirement to use narcotics for analgesia is prohibited and exclusionary. The use of acetaminophen (two

	0
EmitBio Inc.	Version: 3.1
EB-P30-01	7 February 2024

500mg tablets every 4-6 hours) as an antipyretic is allowed, but must be captured as a concomitant medication, if used.

- Medications to treat chronic medical disorders must not be in a period of adjustment or alteration within 30 days prior to enrollment. If medications have been adjusted within the past 30 days, or are currently being adjusted, this constitutes a chronic medical condition not under adequate control and is exclusionary.
- Measure oxygen saturation at rest via pulse oximeter. Oxygen saturation at rest should be measured after the study subject has been in a sitting position for 5 minutes. Hands should be warm and resting in the lap. Any fingernail polish must be removed prior to obtaining readings. Readings are taken three times over a 10 minute period and the average value recorded. This procedure should be used by study subjects during selfassessments at home.
- Measure vital signs (HR, BP, RR, and oral temperature) and height and weight for determination of BMI. Vital signs at rest should be measured after the study subject has been in a sitting position for 5 minutes. Readings are taken three times over a 10 minute period and the average value recorded. RR and HR should be measured over a full 60 second period. This procedure should be used by study subjects during selfassessments at home.
- Assess dyspnea on exertion: have potential study subject walk in place for 30 seconds; have the subject sit down and wait 30 seconds and measure RR and oxygen saturation. If $RR \ge 20/min$ and $SpO_2 < 96\%$, then individual is excluded from the study.
- Perform full physical examination which will include assessments of the following organs and organ systems: skin, head, ears, eyes, nose, and throat (HEENT), neck, lungs, heart, liver, spleen, abdomen, extremities, lymph nodes (axillary and cervical), and nervous system.
- Obtain urine for pregnancy testing in fecund females
- Review inclusion and exclusion criteria. For clarification, subjects who are
 participating in other diagnostic or observational clinical studies are not prohibited
 from participation based on the exclusion criteria, "Currently enrolled in or plans to
 participate in another clinical trial with a therapeutic investigational agent for any
 medical indication that will be received during the study period."

The overall eligibility of the individual to participate in the study will be assessed once all screening values are available. The screening process can be suspended prior to complete assessment at any time if exclusions are identified by the study team.

Individuals with a diagnosis of COVID-19 severity greater than mild or, signs and symptoms present for more than 72 hours are not eligible for enrollment.

	Page 39 of 70
EmitBio Inc.	Version: 3.1
EB-P30-01	7 February 2024

Individuals who qualify for inclusion will be immediately randomized for their day 1 visit.

BP, pulse, and respiration should be measured 3 times over an approximate 10 minute period. The average of the 3 measurements constitutes the value to be captured on the e-CRF an EDC. It is important that BP cuffs and sphygnomonometers are adequately sized and calibrated.

An individual may be re-screened if a protocol eligibility criterion, that is not met at the initial time of screening, will be met by rescreening of all assessments within the next 24 hours using the same subject number, provided their number of days since symptom onset remains 72 hours or less.

No individual may be screened more than twice due to a screening failure result as defined above.

Individuals will be provided the results of any screening abnormality necessitating follow-up with their primary care provider.

